6. ANALYSES AND SUMMARIES

Unless otherwise specified, all analyses will be carried out using the Censored Analysis Set as defined in Section 4.

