# 7. DISCONTINUATION OF STUDY INTERVENTION AND PARTICIPANT DISCONTINUATION/WITHDRAWAL

#### 7.1. Discontinuation of Study Intervention

It may be necessary for a participant to permanently discontinue study intervention. Reasons for permanent discontinuation of study intervention may include the following:

- Progression of underlying disease such that the investigator no longer considers participation appropriate, or of potential benefit to the participant.
- Hospitalization that in the opinion of the investigator would render continued participation unfeasible.
- If a participant experiences Grade 3 AEs judged by the Investigator as related to randomized study intervention, the study intervention will be temporarily discontinued until the treatment-related AEs return to Grade 2 (or less). If the treatment-related AEs return to Grade 2 (or less) or resolve within 4 weeks, continuation of dosing with study intervention may be considered. If these AEs do not return to Grade 2 (or less) within 4 weeks, and after discussion with the sponsor, the participant will be permanently discontinued from the study intervention.

- If a participant experiences Grade 4 AEs judged by the Investigator as related to randomized study intervention, the participant will be permanently discontinued from the study intervention.
- Severe allergic reaction to study intervention.
- Intent to become pregnant or pregnancy confirmed by b-hCG testing.
- Drug-induced liver injury as described in Section 10.6, Appendix 6.

Note that discontinuation of study intervention does not represent withdrawal from the study. If study intervention is permanently discontinued, the participant should remain in the study to be evaluated for follow up. All cases of planned or potential discontinuation of study intervention should be discussed with Sponsor before classifying a subject as 'Discontinued from Study Intervention' and completing an Early Termination visit. See the SoA for data to be collected at the time of discontinuation of study intervention and follow-up for any further evaluations that need to be completed.

In the event of discontinuation of study intervention, it must be documented on the appropriate CRF/in the medical records whether the participant is discontinuing further receipt of study intervention or also from study procedures, posttreatment study follow-up, and/or future collection of additional information.**Follow-Up:** 

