#### 8.3.7. Imaging Assessment-CT Scan

#### 8.3.7.1. Imaging Safety Assessment

CT scans will be acquired during the study to monitor the tumor burden. All CT scans will need to include chest, abdomen, and pelvis to be acceptable for this study.

If SOC CT scan with chest, abdomen, and pelvis was performed within 3 weeks prior to the Screening the visit, then a CT scan at Screening is not needed. If a SOC CT scan is being performed at the Week 12 visit, between Weeks 10-12 or within 7 days after the Week 12

visit as part of SOC, then an additional CT scan is not needed. Similarly, if SOC CT scan is performed 2 weeks prior or 7 days after the ED visit, then an additional CT scan is not needed.

Monitoring of the tumor burden will be performed by the site following standard RECIST 1.1 criteria (outlined in Appendix 11). The RECIST 1.1 categorization is to be entered in the CRF after each scan.

All follow up testing and final diagnosis will be left to the discretion of the medical professionals at the site or those with an existing physician participant relationship. The PI will be responsible for reporting any AEs identified from incidental findings as described in the AE reporting section.

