Pharmacokinetics	To evaluate PK of ponsegromab following repeated SC administration to participants with cancer cachexia and elevated concentrations of GDF-15.	Serum unbound and total concentrations of ponsegromab on Day 1, Week 4, 5, 8, 10 12, and 16, plus Week 9 and 11 in PK substudy only.	Not Applicable.
Biomarkers	To evaluate the effect of repeated SC administration of ponsegromab on circulating GDF-15 concentrations in participants with cancer cachexia, and elevated concentrations of GDF- 15.	Serum unbound and total concentrations of GDF-15 on Day 1, Week 4, 5, 8, 10, 12, and 16, plus Week 9 and 11 in PK substudy only.	Not Applicable.
Immunogenicity	To evaluate the immunogenicity profile of ponsegromab following repeated SC administration in participants with cancer cachexia, and elevated concentrations of GDF-15.	Incidence of ADA and NAb.	Not Applicable.
Efficacy	To evaluate the effect of ponsegromab compared to placebo on Patient- Reported Outcomes Version PROMIS-Fatigue questionnaire in participants with cancer, cachexia, and elevated concentrations of GDF- 15.	Change from baseline score for PROMIS-Fatigue at Week 12.	Not Applicable.
Efficacy	To evaluate the effect of ponsegromab compared to placebo on PROMIS Physical Function-Short Form 8c in participants with cancer, cachexia, and elevated concentrations of GDF- 15.	Change from baseline score for PROMIS-Physical Function at Week 12.	Not Applicable.
Efficacy	 To evaluate the effect of ponsegromab compared to placebo on PGI-S and 	 Change from baseline PGI-S at week 12; PGI-C at Week 12. 	Not Applicable.

	PGI-C (appetite, fatigue, physical function, physical activity and walking) in participants with cancer, cachexia, and elevated concentrations of GDF-15.		
Efficacy	To evaluate the effect of ponsegromab compared to placebo on tumor burden and tumor status in participants with cancer, cachexia, and elevated concentrations of GDF-15.	Tumor status according to RECIST 1.1 guidelines using CT scan at Week 12.	Not Applicable.
Efficacy	To evaluate the effect of ponsegromab compared to placebo on body composition as measured by CT scan in participants with cancer, cachexia, and elevated concentrations of GDF- 15.	Change from baseline in LSMI derived from CT scans at Week 12; Percent change from baseline in skeletal muscle and adipose tissue measures derived from CT scans at Week 12.	Not Applicable

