4. ANALYSIS SETS (POPULATIONS FOR ANALYSIS)

Data for all participants will be assessed to determine if participants meet the criteria for inclusion in each analysis population prior to unblinding and releasing the database and classifications will be documented per standard operating procedures.

Participant Analysis Set	Description
Enrolled	"Enrolled" means a participant's, or their legally authorized representative's, agreement to participate in a clinical study following completion of the informed consent process and randomization to study intervention. A participant will be considered enrolled if the informed consent is not withdrawn prior to participating in any study activity after Screening. Potential participants who are screened for the purpose of determining eligibility for the study, but do not participate in the study, are not considered enrolled, unless otherwise specified by the protocol.
Evaluable	All participants randomly assigned to study intervention and who take at least 1 dose of study intervention. Participants will be analyzed according to the randomized intervention.
Safety analysis set	All participants randomly assigned to study intervention and who take at least 1 dose of study intervention. Participants will be analyzed according to the study intervention they actually received. This will be the study intervention received by the participant for the majority of the timepoints during the relevant part of the study. If a participant receives an equal number of different doses, then the lowest of those doses will be used. If a participant receives an equal number of placebo and a given dose of ponsegromab, the ponsegromab dose will be used.

Defined Analysis Set	Description
Censored	All evaluable participants. For participants who discontinue study intervention, or receive a prohibited procedure or prohibited medication, all observations post-discontinuation, or post-procedure, will be censored and treated as missing data. For participants who miss a dose, or receive an incomplete dose, all observations post-missed/incomplete dose will be censored and treated as missing data.
Complete	All evaluable participants. For participants who discontinue study intervention, receive a prohibited procedure or prohibited medication, and/or miss a dose,

Defined Analysis Set	Description
	or receive an incomplete dose, all observations post- discontinuation, post-procedure or post- missed/incomplete dose will be included in the analysis set.

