6.2.4. Incidence of adverse events, safety laboratory tests, vital signs and ECG abnormalities

Analysis of adverse events, laboratory abnormalities, vital signs and ECG abnormalities will use the Safety Analysis Set defined in Section 4.

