Absolute values and changes from baseline in PGI-S will be summarized descriptively by treatment group and timepoint as described in Section 5.2.2.

6.4.9. Tumor status according to RECIST 1.1 guidelines using CT scan at Week 12

The overall tumor response will be summarized by treatment, as described in Section 5.2.2, using the categories defined in Appendix 11 of the protocol.

6.4.10. Change from baseline in LSMI derived from CT scans at Week 12; Percent change from baseline in skeletal muscle and adipose tissue measures derived from CT scans at Week 12

Absolute values and changes from baseline in LSMI will be summarized descriptively by treatment group and timepoint, as described in Section 5.2.1.

Change from baseline in LSMI will be analyzed using ANCOVA as described in Section 5.2.5. Additional terms for type of therapy [i.e. platinum or not] and type of cancer will be fitted in the model.

Absolute values and percent changes from baseline in skeletal muscle and adipose tissue measures (listed in Section 3.4.10) will be summarized descriptively by treatment group and timepoint, as described in Section 5.2.1.

6.4.11. Change from baseline albumin and pre-albumin levels at Week 12

Absolute values and fold changes from baseline in albumin and pre-albumin will be summarized descriptively by treatment group and timepoint, as described in Section 5.2.1.

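### Tumour status inherits the SAP's default Censored set, so some collected scans are treated as missing for reasons that may be linked to progression

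*SAP*

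**What the plan says.** SAP Section 6 sets a default for everything below it: "Unless otherwise specified, all analyses will be carried out using the Censored Analysis Set as defined in Section 4". SAP 6.4.9 then describes the tumour summary in one sentence, "The overall tumor response will be summarized by treatment, as described in Section 5.2.2, using the categories defined in Appendix 11 of the protocol", and names no analysis set.

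SAP Section 4 defines the Censored set. After discontinuation of study intervention or a prohibited procedure or medication, "all observations post-discontinuation, or post-procedure, will be censored and treated as missing data"; a similar sentence covers a missed or incomplete dose. The same section dates discontinuation at the last dose plus 29 days.

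The endpoint in SAP 2.2 is "Tumor status according to RECIST 1.1 guidelines using CT scan at Week 12". It is typed as efficacy and its estimand is given as not applicable. SAP 6.2.4 limits the Safety set: "Analysis of adverse events, laboratory abnormalities, vital signs and ECG abnormalities will use the Safety Analysis Set defined in Section 4". Protocol 8.3.7.1, headed as an imaging safety assessment, says: "CT scans will be acquired during the study to monitor the tumor burden". Protocol 7.1 lists as its first reason for stopping drug: "Progression of underlying disease such that the investigator no longer considers participation appropriate, or of potential benefit to the participant".

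**The concern.** The Censored set implements Estimand 1, a hypothetical question about body weight with all doses given and no confounding treatment. Nobody posed that question for tumour status, which has no estimand. Its stated objective is the effect of ponsegromab on tumour burden and status.

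For that objective, stopping drug is not a nuisance to be removed. A participant may stop because the tumour has progressed, and a later scan is then the evidence of progression. Missing a dose can also accompany clinical decline, and it censors every later observation, even if dosing resumes and a valid Week 12 scan is taken. If such events differ by arm, the table could show too small or too large a difference in progression. The same summary is listed for the interim analysis, whose results SAP 7.1 says may inform stopping or adaptation.

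**Working it through.** **1. Does the default reach this table?** Where the SAP wants another set it says so: Safety in 6.2.4, PK in 6.4.3, PD (pharmacodynamic) in 6.4.4, Immunogenicity in 6.4.5, and Complete for body weight in 6.1.1.2. Section 6.4.9 says nothing, and no Complete-set tumour table is planned. The Censored set therefore applies. SAP 7.2.1 refers back to 6.4.9 for the interim.

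**2. Which scans are lost?** With doses on Days 1, 29 and 57, the discontinuation dates are:

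- last dose Day 1: 1 + 29 = Day 30
- last dose Day 29: 29 + 29 = Day 58
- last dose Day 57: 57 + 29 = Day 86

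The protocol schedules CT at Week 12 (Day 85) and at the ED visit. It accepts a standard-of-care (SOC) scan from 2 weeks before to 7 days after the ED visit.

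- Kept: an ED scan up to the cut-off, and a Day 85 scan after three complete doses, provided no other censoring event came first.
- Lost: an ED or SOC scan past the cut-off; a Week 12 scan in someone who stopped after dose 1 or 2; any scan after a missed or incomplete dose or a prohibited procedure.
- Unclear: scans after a prohibited medication. The Section 4 sentence names medication as a trigger but censors only post-discontinuation and post-procedure observations. Estimand 1 (SAP 2.2.1) does censor after medications judged to modulate body weight.

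**3. How many participants could be affected?** Protocol 9.5 plans 168 randomized (42 per arm) for about 120 completers at about 30% discontinuation. Check: 120 / 0.70 = 171.4 and 168 × 0.70 = 117.6, so the plan's figures agree approximately. Discontinuers per arm: 42 × 0.30 = 12.6, or about 50 of 168 overall.

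**4. How large could the effect be?** Let *d* be the share with a censoring event, *r* the share of their scans that is kept, and *pc* and *pe* the progression rates without and with such an event.

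- All scans: (1 − d)·pc + d·pe
- Censored set: [(1 − d)·pc + d·r·pe] / [(1 − d) + d·r]

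The documents give no progression rate and no *r*. Assumptions: d = 0.30 (the discontinuation rate as a stand-in), pc 20–40%, pe 40–80%, and every participant scanned.

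At the extreme, pc = 20% and pe = 80%, the all-scans rate is 0.7 × 0.2 + 0.3 × 0.8 = 38.0%. The censored rate is:

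- r = 0: 20.0%
- r = 0.5: (0.14 + 0.12) / 0.85 = 30.6%
- r = 0.9: (0.14 + 0.216) / 0.97 = 36.7%

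Over the whole grid:

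| Share of scans kept (r) | Understatement of progression | Progression cases lost per arm, 12.6 × (1 − r) × pe |
|---|---|---|
| 0 | 0 to 18 points | 5.0 to 10.1 |
| 0.5 | 0 to 7.4 points | 2.5 to 5.0 |
| 0.9 | 0 to 1.3 points | 0.5 to 1.0 |

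The zero occurs when pc = pe.

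**5. Arms with different censoring.** Take d = 20% against 40%, pc = 30%, pe = 60%. All scans: 36.0% against 42.0%, a difference of 6.0 points. With r = 0.5: 0.30/0.90 = 33.3% against 0.30/0.80 = 37.5%, a difference of 4.2. With r = 0: 30.0% in both arms, a difference of 0.

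**The case against.** A reader might infer that every scan after stopping drug is thrown away. The documents do not support that: the 29-day rule keeps many ED scans, often those closest to the decision to stop. Protocol 7.1 follow-up after discontinuation lists concomitant treatments, vital signs and adverse events but not CT, so few scans past the cut-off may exist. The clearer exposure is a participant who missed a dose but stayed in the study.

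A reader might also infer that tumour status already belongs to the safety population, because the protocol places CT under safety. The sentence on safety analyses in Protocol 9.3.3 sits in the row for adverse events, laboratory tests, vital signs and ECG, and SAP 6.2.4 has the same scope. That argument falls.

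The medication limb is weak as well. It rests on Estimand 1 wording, is limited to drugs affecting body weight and depends on blinded review; Protocol 6.9.1 permits stable steroids and some short-term symptomatic use.

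The stakes are limited. The table is tertiary and descriptive, and SAP 5.1 does not list tumour status among the tested endpoints. Discontinuations and changes to anti-cancer therapy are reported by arm elsewhere, which would partly expose an imbalance. Changing the set alone would also not settle whether an ED scan counts as Week 12.

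These points narrow the concern. They do not remove it: a stated rule still sets aside scans already taken, for reasons that can be tied to the outcome, on an endpoint for which the rule was not designed.

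**Conclusion.** The concern holds in a limited form. The Censored set governs the tumour-status table and its interim counterpart by default, and the loss of scans may be informative. That progression will be undercounted, or that a false difference between arms will appear, is a possibility and not a finding. It requires progression rates to differ between participants with and without a censoring event, and enough of the affected scans to be lost. A distorted comparison additionally needs the arms to differ in censoring, in scans kept or in those rates.

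The 0 to 18 point range rests on assumed progression rates and shares of scans kept; only 42 per arm and 30% come from the protocol. The upper end needs every affected scan to be lost, which the 29-day rule makes unlikely for discontinuers. Missed doses among those who stay would raise *d*; discontinuers never scanned would lower it. This is a cheap improvement to an exploratory table and has no bearing on the primary analysis.

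**What to change.** In SAP 6.4.9 and the RECIST sentence of 7.2.1:

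- Specify the Complete analysis set, so that all collected post-baseline scans up to the Week 12 window count regardless of intercurrent events.
- State how ED and SOC scans map to Week 12. The protocol already accepts SOC scans from Week 10 to 7 days after the Week 12 visit.
- Show by arm the number without an assessment, and state the denominator of the percentages.

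Separately, reconcile the Section 4 wording with Estimand 1 on observations after a prohibited medication.

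Cost: a few sentences, one table re-specified for the final and interim outputs, and a little programming for the scan mapping. No new data are needed, because the protocol has the RECIST category entered in the CRF after each scan. The downside is that the table will include off-treatment scans, which a footnote should say.

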6.1. Primary Endpoint(s)

6.1.1. Change from baseline body weight at Week 12

6.1.1.1. Main Analysis

Absolute values, changes from baseline and percent changes from baseline in body weight will be summarized descriptively by treatment group and timepoint, as described in Section 5.2.1. Tables will include baseline and all post-baseline timepoints. Box and whisker plots (or similar) of absolute values, changes from baseline and percent changes from baseline over time will also be produced, with all treatments on the same plot.

Change from baseline in body weight will be analyzed using an MMRM model as described in Section 5.2.3. All post-treatment dosing timepoints up to Week 12 (ie. Weeks 4, 8 and 12) will be included in the model. Additional terms for type of therapy [i.e. platinum or not] and type of cancer will be fitted in the model. Additional plots of LS means and differences (including 90% CIs for both), for Week 12 only, will be produced over treatment.

A Bayesian E_{max} model, as described in Section 5.2.4, will then be fitted to the Week 12 LSmeans and SEs from the MMRM analysis. This will be used to estimate the treatment effect related to the primary Estimand 1 (as described in Section 2.2.1). If the E_{max} model analysis is not performed, the primary results for the study will be based on the MMRM results at Week 12.

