#### 4.2. Scientific Rationale for Study Design

The purpose of this study is to evaluate the efficacy, safety, and tolerability of ponsegromab, an inhibitor of GDF-15, compared to placebo, in patients with cancer, cachexia, and elevated concentrations of GDF-15.

Elevated concentrations of circulating GDF-15 have been reported in literature in patients experiencing weight loss with a variety of tumor types and a greater magnitude of elevation was associated with worse survival. Biospecimens from healthy adults (n=739) and patients with cancer (from both external commercial biorepositories and an internal study) were analyzed for GDF-15 concentrations. The cancer sample set contained 399 NSCLC, 116 pancreatic cancer, and 157 colorectal cancer patients. Analysis of both the cancer and healthy sample sets using the Roche Elecsys assay, confirmed literature reported elevations in GDF-15 concentrations in NSCLC, PANC, and CRC patients in comparison to healthy subjects (approximately 4-fold, 5-fold, and 4-fold, respectively). An ad-hoc analysis of samples from NSCLC patients from an internal Pfizer study demonstrated that higher GDF-15 concentrations were associated with a reduction in body weight. These data were also used to determine the GDF-15 inclusion criteria for this study to be the 95th percentile of GDF-15 concentrations reported in these healthy subjects (≥1.5 ng/mL).

In addition, published clinical data and internal animal model data suggest that administration of platinum therapy can induce increases in serum GDF-15 concentrations. Clinical literature and internal animal model data also suggest that the nausea, emesis and anorexia observed with platinum therapy may be mediated, at least in part, by platinum induced- elevations in GDF-15.

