#### 4.3. Justification for Dose

In the part A of this study, ponsegromab will be administered with 100, 200, or 400 mg Q4W SC for a total of 3 doses. The proposed doses were determined based on all relevant information obtained from nonclinical safety studies and clinical data (including safety, tolerability, PK and PD) available. These clinical data included data from 2 completed studies in healthy participants (C3651001 and C3651002, see IB), clinical data (including safety, tolerability, PK, and PD) from the phase 1b study in cancer cachexia patients (C3651009), and the expected duration of GDF-15 suppression, defined as the time it suppress GDF-15 to below the median observed in healthy subjects (0.71 ng/mL).

The median baseline GDF-15 in NSCLC, PANC, and CRC patients are expected to be approximately 3.02, 3.32, and 3.50 ng/mL, respectively, and the 95th percentile are expected to be 8.69, 9.35, and 13.4 ng/mL, respectively. It is assumed that the composition of the cancer types will be similar to that observed in study C3651009, which is 4:4:3 for NSCLC, CRC, and PANC, respectively. Based on preliminary population PK/PD simulations, the proposed 100 mg Q4W SC dose is expected to suppress the unbound GDF-15 concentration in ~64%, and ~28% of the assumed cancer cachexia patients for 2, and 4 weeks, respectively. The proposed 200 mg Q4W SC dose is expected to suppress the unbound GDF-15 concentration in ~92%, and ~72% of the cancer cachexia patients for 2, and 4 weeks, respectively. The proposed high dose of 400 mg Q4W SC dose is expected to suppress the unbound GDF-15 concentration in >90% of the cancer cachexia patients for 4 weeks.

Based on these preliminary PK/PD simulations, the predicted steady state total ponsegromab Cmax, AUCtau, and Cavg, following 100, 200, and 400 mg Q4W SC doses, along with the corresponding safety margins calculated using exposure data from the 6-month toxicology study in monkeys (See IB), and exposure multiples calculated using total exposure data following a single 300 mg SC dose to healthy participants in study C3651001 are summarized in Table 3. The corresponding steady state unbound ponsegromab exposures and exposure multiples calculated using unbound exposure data from study C3651001, are summarized in Table 4.

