## 9.5. Sample Size Determination

A sufficient number of participants will be screened to achieve a total of approximately 168 participants, with 42 participants randomly assigned to ponsegromab 100, 200 or 400 mg and placebo in approximately a 1:1:1:1 ratio. This is expected to ensure completion through Week 12 of the study of approximately 120 completing participants (30 in each of ponsegromab 100, 200 or 400 mg and placebo), assuming a discontinuation rate of approximately 30% (if this rate is higher, or there is a high rate of non-compliance, more participants may be randomized to ensure the required number of completing participants).

The sample size in the ponsegromab and placebo arms is based on the primary efficacy endpoint, mean change from baseline in body weight at Week 12. An informative meta-analytic predictive prior, based on historical results from internal and external studies, robustified by the inclusion of a weakly informative component to handle any possible prior-data conflict, will be used for the placebo response and is expected to equate to an effective sample size of 39 placebo participants. Further details on the prior derivation will be given in the statistical analysis plan SAP.

120 completing participants, in a 1:1:1:1 ratio, plus 39 participants from the placebo prior, gives acceptable Operating Characteristics in that:

- The probability of achieving statistical significance (at the 5% significance level, using a 1-sided t-test), for a true difference between ponsegromab and placebo of 2.7 kg, is approximately 80%.
- An observed difference between ponsegromab and placebo of 1.8 kg is expected to achieve statistical significance (at the 5% significance level, using a 1-sided t-test).

A conservative estimate of the standard deviation, for the change from baseline in body weight at 12 weeks of 4.9 has been used.

The sample size determination has been performed using pairwise comparisons. This is considered to be a conservative approach since the primary analysis will utilize a Bayesian  $E_{max}$  dose-response model, which would be anticipated to best describe the dose-response in the presence of an effective compound.

Evaluable participants are defined as in Section 9.2. Participants who withdraw from the study will not be replaced.

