5. GENERAL METHODOLOGY AND CONVENTIONS

5.1. Hypotheses and Decision Rules

The null hypothesis of no difference between ponsegromab and placebo will be tested for each primary, and selected secondary (physical activity, FAACT and CRCSD) and tertiary (PROMIS-fatigue, PROMIS-physical function, LSMI and survival status) endpoints. The alternative hypothesis is that ponsegromab is superior to placebo. The Type I error rate (α-level) used for the statistical inference will be 5% (1-sided). Each dose of ponsegromab will be compared separately with placebo. No adjustment for multiple comparisons will be made.

For all other endpoints, the results of any statistical analyses are for exploratory purposes only and there is no formal hypothesis testing.

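### The primary body-weight MMRM does not adjust for screening GDF-15, a cheap efficiency gain of unknown, probably small to moderate, size

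*SAP*

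**What the plan says.** The MMRM in SAP 5.2.3 fits baseline, time, baseline-by-time, treatment and treatment-by-time. For body weight, SAP 6.1.1.1 adds: "Additional terms for type of therapy [i.e. platinum or not] and type of cancer will be fitted in the model". Protocol 9.3.2 names the same two extra terms. SAP 5.2.3 allows further terms where appropriate, but its examples do not include GDF-15.

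Screening GDF-15 of at least 1.5 ng/mL on the Roche assay is an inclusion criterion (protocol 5.1). Protocol 4.2 cites literature on raised GDF-15 in patients losing weight, and an ad hoc internal analysis of NSCLC samples in which "higher GDF-15 concentrations were associated with a reduction in body weight". It gives no coefficient. Protocol 4.3 expects median values of 3.02, 3.32 and 3.50 ng/mL in NSCLC, PANC and CRC, and adds that "the 95 th percentile are expected to be 8.69, 9.35, and 13.4 ng/mL, respectively". Randomisation is stratified by platinum use only, because of the link between platinum and GDF-15 (protocol 4.2).

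The SAP does use screening GDF-15 elsewhere. Section 6.5 fits a body-weight MMRM with GDF-15 split at the study median and interacting with treatment and time, and plots GDF-15 against Week 12 weight change. Section 6.6.1 summarises it at baseline.

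On size, protocol 9.5 counts "120 completing participants, in a 1:1:1:1 ratio, plus 39 participants from the placebo prior" and says power "for a true difference between ponsegromab and placebo of 2.7 kg, is approximately 80" per cent. On variability it says: "A conservative estimate of the standard deviation, for the change from baseline in body weight at 12 weeks of 4.9 has been used".

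**The concern.** When a baseline variable predicts the outcome and is left out of the model, its contribution stays in the residual variance. Here that variance enters the standard errors of the Week 12 LS means, which are the input to the Bayesian Emax model.

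GDF-15 is a natural candidate. It is the drug's target, it is measured before randomisation in everyone eligible, and the protocol itself associates it with body weight. The covariates already fitted are imperfect substitutes. The three expected medians differ by at most 0.48 ng/mL (3.50 - 3.02), while the 95th percentiles lie 5.67 to 9.9 ng/mL above them, so most of the spread is within cancer types. Platinum use is a yes/no correlate of the measured quantity.

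The subgroup model in SAP 6.5 reports effects within GDF-15 halves. It does not report one overall effect adjusted for GDF-15. If the arms turned out unequal in GDF-15, an adjusted estimate first produced after unblinding would be a post hoc choice. Naming the analysis in advance avoids that.

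**Working it through.** **Inputs.** SD 4.9 kg, true difference 2.7 kg, 30 completers per arm and a placebo prior worth 39 participants, all from protocol 9.5 and taken as stated. One-sided 5% level from SAP 5.1. The partial correlation r between log screening GDF-15 and 12-week weight change, given the terms already fitted, is **not in the documents**. A range of 0.1 to 0.4 is assumed.

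**1. Reproduce the plan's figures.** A pairwise comparison has 30 on a dose against 30 + 39 = 69 on placebo.

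- SE = 4.9 × √(1/30 + 1/69) = 1.072 kg.
- Power = Φ(2.7/1.072 - 1.645) = 80.9%. The noncentral t version with 97 degrees of freedom gives 80.4%. The protocol says about 80%.
- Smallest significant difference = t(0.95, 97) × 1.072 = 1.78 kg. The protocol says 1.8 kg.

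Both figures reproduce without GDF-15 in the model.

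**2. Add the covariate.** The residual SD in the trial data becomes s = 4.9 × √(1 - r²). The historical placebo information is described in protocol 9.5 as a prior that "is expected to equate to an effective sample size of 39 placebo participants". A covariate fitted in this trial cannot sharpen it, so its variance stays at 4.9²/39:

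SE(r) = √[ s²/30 + 1/(30/s² + 39/4.9²) ], and power = Φ(2.7/SE(r) - 1.645).

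Example at r = 0.2: s² = 24.01 × 0.96 = 23.05. SE = √[0.768 + 1/(1.302 + 1.624)] = √(0.768 + 0.342) = 1.054 kg. Power = Φ(2.563 - 1.645) = 82.1%.

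| Assumed r | Residual SD (kg) | Power at 2.7 kg, prior fixed | Trial-only SE, 30 vs 30 (kg) | Equivalent gain in trial sample size |
|---|---|---|---|---|
| 0 | 4.900 | 80.9% | 1.265 | 0% |
| 0.1 | 4.875 | 81.2% | 1.259 | 1% |
| 0.2 | 4.801 | 82.1% | 1.240 | 4% |
| 0.3 | 4.674 | 83.5% | 1.207 | 10% |
| 0.4 | 4.491 | 85.6% | 1.160 | 19% |

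The trial-only SE is s × √(2/30), and the sample-size gain is 1/(1 - r²) - 1.

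**3. Chance imbalance.** If two arms of 30 differ in log GDF-15 by one standard error of the between-arm difference, the unadjusted weight difference moves by r × 4.9 × √(2/30): 0.13, 0.25, 0.38 and 0.51 kg at r = 0.1, 0.2, 0.3 and 0.4. This is not additional to step 2. At r = 0.3, 1.265² - 0.38² = 1.600 - 0.144 = 1.456, and √1.456 = 1.207 kg, the adjusted SE in the table. The imbalance is the same variance in another form.

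**The case against.** The strongest reply is that nothing is wrong with the planned model. Randomisation makes the comparison unbiased whether or not GDF-15 is fitted. The power target is met with an SD the protocol calls conservative, using pairwise tests it regards as conservative relative to the Emax model. Platinum is stratified and fitted because of its link with GDF-15, and SAP 6.5 already brings GDF-15 into a body-weight MMRM. All of this stands, except that SAP 6.5 does not yield an overall adjusted effect.

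The evidence that GDF-15 predicts the outcome is also thin. The internal analysis is ad hoc and in one tumour type, and the protocol does not show that GDF-15 predicts later 12-week change. This trial restricts the range by requiring at least 1.5 ng/mL and prior weight loss. Terms already in the model may carry part of the information, so the relevant r is a partial correlation. At r = 0.1 the gain is 0.3 percentage points. This stands too, and is why only a range can be shown.

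The mechanism cuts against a common slope. Ponsegromab blocks GDF-15, three of the four arms are active, and protocol 4.3 expects 400 mg to suppress it for 4 weeks in more than 90% of patients. The slope could flatten or reverse on treatment, and a single GDF-15 term would then recover little. This stands as a limit on the gain, not as a reason against prespecifying the term.

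A reader might infer more than the documents support. Omitting the covariate does not bias the result, raise type I error or leave the trial short of its stated power. A chance imbalance is not a second harm on top of lost precision (step 3). Scaling all 69 placebo participants by √(1 - r²) would give 82.3%, 84.1% and 86.5% at r = 0.2, 0.3 and 0.4, but that credits the covariate with sharpening historical data it cannot touch.

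**Conclusion.** The point holds as a low-cost improvement, not as an error in the plan. The primary MMRM omits a baseline value that every eligible participant has and that the protocol associates with body weight, and no planned analysis supplies an overall effect adjusted for it. That much is certain from the documents.

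The size of the gain is not. Over the assumed range of r from 0.1 to 0.4, power at 2.7 kg rises by 0.3, 1.2, 2.6 and 4.7 percentage points from 80.9%. These figures assume an SD of 4.9 kg, 30 completers per arm, a prior worth 39 participants that the covariate does not sharpen, and the same GDF-15 slope in every arm. If the slope differs between placebo and active arms, the gain could be smaller.

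**What to change.** Before unblinding, add log(screening Roche GDF-15) and its interaction with time as covariates in the body-weight MMRM of SAP 6.1.1.1, and in the percent-change MMRM of SAP 6.1.1.2. Report the current model as a sensitivity analysis. Because SAP 7.2.1 runs the 6.1.1.1 analysis at any interim, the decision should be made by staff who have not seen interim results by arm.

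The cost is SAP wording and about three degrees of freedom (one slope at each of Weeks 4, 8 and 12). No new data are needed, and values should be complete because they decide eligibility. The covariates are also named in protocol 9.3.2, and both protocol section 9 and SAP section 2 require a major modification of the primary analysis to appear in a protocol amendment. If the sponsor judges this to be one, an amendment is needed.

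If the sponsor prefers not to change the primary model, the minimum is to prespecify the GDF-15-adjusted MMRM as a sensitivity analysis in SAP 6.1.1.2.
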